3.1.3. Exploratory (if applicable)

- Assess the EBOV neutralizing antibody titers by study group.
- Assess antibody functionality by antibody-dependent cell-mediated cytotoxicity (ADCC) responses by study group.
- Assess activation of CD4+ and CD8+ T cells in multiple cell subpopulations by study group.
- Assess inflammation via cytokine secretion and C-reactive protein (CRP) by study group.
- Assess EBOV GP-specific T cell responses by study group.
- Assess ChAd3-specific T cell responses by study group.
- Assess plasmablast frequencies by study group.
- Assess B-cell receptor (BCR) repertoire by study group.
- Assess and characterize change in gene expression in PBMCs by study group.
- Identify gene expression changes associated with adaptive humoral and/or cellular immune responses.

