5.4. Treatment Assignment Procedures

5.4.1. Randomization Procedures

Per International Council for Harmonisation of Technical Requirements for Pharmaceuticals for Human Use (ICH) guideline E6: Good Clinical Practice (GCP), screening records will be kept at the participating VTEU site to document the reason why an individual was screened, but failed trial entry criteria. The reasons why individuals failed screening will be recorded in the Statistical and Data Coordinating Center's AdvantageEDCSM (Electronic Data Capture System).

Once consented and upon entry of demographic data and confirmation of eligibility for this trial, the subjects will be enrolled. Subjects will be randomized 1:1:1 in double-blind fashion to 1 dose of ChAd3-EBO-Z vaccine at Day 1 followed by a booster of placebo, ChAd3-EBO-Z (homologous), or MVA-BN®-Filo (heterologous) at Day 8.

Enrollment of subjects will be done online using the enrollment module of AdvantageEDCSM. The randomization code will be prepared by statisticians at the SDCC and included in the enrollment module for this trial. AdvantageEDCSM will assign each subject to a treatment arm after the demographic and eligibility data have been entered into the system. A designated individual at the participating VTEU site will be provided with a code list for emergency unblinding purposes, which will be kept in a secure place.

Instructions for use of the enrollment module are included in the AdvantageEDCSM User's Guide. Manual back-up randomization procedures and instructions are provided for use in the event that a participating VTEU site temporarily loses access to the Internet or the online enrollment system is unavailable.

Subjects who sign the informed consent form (ICF) and are randomized but do not receive study vaccine may be replaced. Subjects who sign the informed consent form, and are randomized and vaccinated, and subsequently withdraw, or are withdrawn or terminated from this trial, or are lost to follow-up may be replaced.

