For the transcriptomics exploratory analysis, RNA-Seq data will be pre-processed by removing adapters and low-quality reads and mapping sequences to the latest human reference genome using splice-aware alignment software such as *HISAT2*³⁵. Gene expression quantification will be carried out by using the *Subread* software³⁶ using the latest Ensembl³⁷ gene model annotations as a reference. Systematic differences in sequence coverage between samples will be accounted for using the TMM method³⁸ as implemented in the *edgeR*³⁹ R package. Principal component analysis, non-metric multidimensional scaling, and hierarchical clustering analysis will be used to identify potential global outliers and systematic batch effect. Negative binomial models as implemented in *edgeR*³⁹ will be used to identify genes for each study group and post-vaccination day that were differentially expressed (DE) compared to pre-vaccination as well as genes that were DE between study groups. If the analysis reveals a systematic batch effect that is not associated with study group, it will be accounted for by adding a batch blocking factor as part of the negative binomial models. To control for testing multiple genes, the false-discovery rate (FDR) based on the Benjamini-Hochberg procedure⁴⁰ as implemented in the *p.adjust* R function will be applied. Genes with a FDR-value < 0.05 and a fold change of greater or equal to 1.5-fold (up or down regulation) will be deemed to be significantly DE. Depending on observed treatment effects, this fold change cut off may be revised. The *pvclust*⁴¹ R package will be applied to identify co-expressed DE gene clusters and cluster time trends will be visualized. Pathway enrichment analysis based on the latest MSigDB⁴² and KEGG⁴³ databases as well as Blood Transcription Modules⁴⁴ accounting for gene length bias will be carried out using the implementation provided by the *goseq*⁴⁵ R package. Pathway maps color-coded by treatment effect will be provided for significantly enriched KEGG pathways. Regularized canonical correlation analysis and regularized linear regression analysis as implemented in the mixOmics⁴⁶ and *glmnet*⁴⁷ R packages, respectively will be utilized to identify gene expression changes that are associated with adaptive humoral and/or cellular immune response endpoints. In both cases, cross-validation will be used to select optimal models.

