11.4.5. Missing Values and Outliers

All attempts will be made to collect all data per protocol.

As missing data are expected to be minimal, no imputation will be performed for missing values. Any data point that appears to be erroneous or inexplicable based on clinical judgment will be investigated as a possible outlier. If data points are identified as outliers, sensitivity analyses will be performed to examine the impact of including or excluding the outliers. Any substantive differences in these analyses will be reported.

For the transcriptomics endpoint, extreme data points will be identified by inspecting global patterns in the data. Experimental meta-data will be examined to see whether the outlying pattern can be attributed to experimental error such as sample mislabeling. Excluded outliers will be documented in the CSR. Due to the complexity, no sensitivity analysis will be carried out for the transcriptomics endpoints.

Please see the separate document **“Statistical Analysis Plan”** for additional information.

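### Module enrichment relies on a yes/no gene list alone, which loses much of the power to find modules whose genes shift together by a modest amount; a full-scale gene-set test should be added beside goseq

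*Protocol*

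**What the plan says.** Protocol 11.4.4 fits negative binomial models in edgeR to every gene, for each post-vaccination day against pre-vaccination and between study groups. Its gene-level rule is "Genes with a FDR-value < 0.05 and a fold change of greater or equal to 1.5-fold", up or down. The next sentence qualifies the second part: "Depending on observed treatment effects, this fold change cut off may be revised". No rule or alternative value is given.

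Enrichment follows: "Pathway enrichment analysis based on the latest MSigDB", together with KEGG and the Blood Transcription Modules, "accounting for gene length bias will be carried out using the implementation provided by the" goseq package. No other module-level test of a shift appears in the protocol or main SAP. Clustering is applied to the differentially expressed genes only, and coloured maps "will be provided for significantly enriched KEGG pathways". In its outlier section, Protocol 11.4.5 adds: "Due to the complexity, no sensitivity analysis will be carried out for the transcriptomics endpoints".

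The objective served is in Protocol 3.1.3: "Assess and characterize change in gene expression in PBMCs by study group". SAP sections 1, 4.5.3, 6.8 and 10 refer the systems-biology detail to a SAP addendum, which is not among the documents available here.

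**The concern.** edgeR gives every gene a continuous estimate and test statistic. goseq uses only whether each gene was called. The protocol does not say in words that the 1.5-fold list is the goseq input, but goseq needs such a list and only one call is defined.

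A module whose genes all move the same way by a modest amount can be clear as a group while few of its genes pass on their own. Such a module could be reported as not enriched. That matters most for the between-arm contrasts on Days 9 and 15, where there are 20 subjects per arm. At stake is part of the hypothesis-generating output that Protocol 11.1 expects from the systems-biology component.

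**Working it through.** The plan states no power or error rate for transcriptomics, so there is no figure to reproduce.

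**From the documents.** FDR below 0.05; 1.5-fold, or log2(1.5) = 0.585; "Subjects will be randomized 1:1:1 in double-blind fashion" with 20 per arm (Protocol 4, Table 1); 60 subjects pooled before the second vaccination (11.4.4).

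**Assumed.** 12,000 genes; a 40-gene module in which every gene shifts equally in one direction; 300 other genes changed 2-fold; per-gene SD 0.6 log2 (also 0.4); between-gene correlation 0.02 to 0.10; module threshold 0.05/346 = 0.000145. Normal log2 data with t-tests stand in for edgeR, and a hypergeometric test stands in for goseq without length weighting.

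**1. Genes needed on the list.** With k of m module genes on a list of L among N genes, p = P(X ≥ k), X hypergeometric(N, L, m). At k = 0, p is exactly 1 whatever the sample size. With N = 12,000, m = 40 and L = 300 + k, k = 6 gives p = 0.00048 and k = 7 gives p = 0.00006. So 7 of the 40 genes must be listed.

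**2. Which cut binds.** With about 300 rejections, the Benjamini-Hochberg cut is near 0.05 × 300/12,000 = 0.00125, or |t| = 3.49 on 38 df. The standard error is SD × √(2/20).
- SD 0.6: SE 0.190, so a gene needs an observed 0.662 log2 (1.58-fold). This exceeds 0.585, so the FDR cut binds.
- SD 0.4: SE 0.126, so FDR needs 3.49 × 0.126 = 0.44 log2 (1.36-fold). The 1.5-fold cut binds.

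**3. Expected genes listed at SD 0.6**, 40 × P(Z > (0.662 − shift)/0.190):
- shift 0.30 (1.23-fold): 1.1 genes
- shift 0.40 (1.32-fold): 3.4 genes
- shift 0.50 (1.41-fold): 7.9 genes

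Against the 7 needed, this predicts almost no power, low power and moderate power.

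**4. Simulated power, 20 v 20, SD 0.6.** The comparator is a camera-type test on all gene statistics with a variance inflation for correlation.

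| True shift | Planned list | Full-scale test |
|---|---|---|
| 1.23-fold | about 0-3% | about 20-99% |
| 1.32-fold | about 10-20% | about 70-100% |
| 1.41-fold | about 60-70% | 98-100% |

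The low ends for the full-scale test belong to correlation 0.10; at 1.23-fold, simulations there ranged from 21% to 43%. At 1.7-fold both tests reached 100%. Null rejection by the full-scale test at nominal 5% was 1% to 3.5%.

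**5. Dropping the fold cut and keeping FDR.** At SD 0.6, power for an FDR-only list against the planned list was 1-2% v 0-1%, 14-23% v 8-22% and 63-78% v 60-72% for the three shifts. At SD 0.4 and 1.32-fold it was 96-99% v 3-7%. This agrees with step 2.

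**6. Pooled data before the second vaccination** (n = 60, 30-gene module, 360 other changed genes, threshold 0.05/300, 40 runs per setting). At 1.3-fold and SD 0.4, all 30 genes passed FDR and on average 0.0 passed 1.5-fold; detection was 0% for the planned list and 100% for the full-scale test. Over SD 0.4 to 0.8 and correlation 0.05 and 0.2, an FDR-only list detected the 1.3-fold module in 98-100% of runs. In one weaker setting (1.2-fold, SD 0.6, correlation 0.2) the FDR-only list found 97.5%, the full-scale test 45% and the planned list 0%.

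**7. Where goseq does better.** For modules with genes moving in both directions, or with only 8 strongly responding genes, the list-based test detected 95-100% and the camera-type test 0-33%.

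**The case against.** - **The governing document is unseen.** Protocol 11.4.4 is a summary, and the addendum may already specify a full-scale test. This stands, and the recommendation is conditional on it.
- **The fold cut may be revised.** This stands in part. At SD 0.4, or with 60 subjects, lowering the cut recovers most modest modules. At SD 0.6 and 20 per arm it recovers little. A change made after seeing the effects, with no stated rule, is also a weaker basis than a test named in advance.
- **The simulated pattern favours the alternative.** A uniform, same-direction shift suits a camera-type test, and step 7 shows the reverse for other patterns. This stands, and it is why goseq should keep equal rank.
- **List-based enrichment is conventional, and the work is exploratory.** True; no formal hypothesis is tested, and the gene-level statistics remain available for later use.

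A reader might infer that any module moving by less than 1.5-fold is missed. That is certain only if every observed fold change in it is below 1.5; a true 1.41-fold module is found in about 60-70% of runs at SD 0.6. A reader might also infer that the first major objective in Protocol 2.2 is compromised. That objective concerns whether early innate responses are associated with later endpoints. Protocol 11.4.4 addresses it by regularized canonical correlation and regularized regression, which do not depend on goseq.

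**Conclusion.** The point holds as a loss of power for one pattern: modules whose genes shift together by a modest amount. At 20 v 20 and SD 0.6, the planned list gives about 0-3%, 10-20% and 60-70% at 1.23-, 1.32- and 1.41-fold, against about 20-99%, 70-100% and 98-100% for a full-scale test. There the gene-level FDR cut causes most of the loss; at SD 0.4 the 1.5-fold cut does.

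The sizes rest on the assumed SD, correlation, module size, uniform shift and number of other changed genes. The exact part is that a module with no listed gene has p = 1. The documents do not support saying that a full-scale test is definitely absent from the plan, or that goseq should be replaced or ranked second. No primary or secondary conclusion is affected. This is a cheap improvement to an exploratory analysis.

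**What to change.** If the SAP addendum does not already contain it, add to Protocol 11.4.4 or the addendum: for each post-vaccination contrast and each between-arm contrast, test the MSigDB, KEGG and Blood Transcription Module sets on all genes with a competitive gene-set test that accounts for between-gene correlation (camera on the fitted edgeR models), with Benjamini-Hochberg adjustment across sets. Report it alongside goseq with equal standing. Keep the FDR and 1.5-fold rule for listing individual genes, and state that this list is the goseq input.

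The models are already fitted, so no new data or samples are needed. The cost is a second enrichment table and a sentence explaining why some modules are found by only one method: coordinated small shifts by the full-scale test, mixed-direction or few-gene responses by goseq.

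### The fold-change cut-off that defines a significant gene may be revised after treatment effects are seen, and transcriptomic outlier exclusions get no with/without re-analysis

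*Protocol*

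**What the plan says.** Protocol section 11.4.4 sets two conditions for a significantly DE gene. The first is an adjusted p-value below 0.05, with multiplicity across genes handled by "the false-discovery rate (FDR) based on the Benjamini-Hochberg procedure". The second is a fold change of at least 1.5 in either direction. The next sentence opens the second condition: "Depending on observed treatment effects, this fold change cut off may be revised". Nothing says who decides, by what criterion, within what limits or by when. The same paragraph then clusters the co-expressed DE genes.

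Section 11.4.5 covers outliers. For transcriptomics, "extreme data points will be identified by inspecting global patterns in the data"; no numeric criterion is given. Two safeguards follow: "Experimental meta-data will be examined to see whether the outlying pattern can be attributed to experimental error such as sample mislabeling", and "Excluded outliers will be documented in the CSR". The section does not say whether an outlying sample with no experimental explanation is kept, or whether the decision is made blind to arm. It closes with "Due to the complexity, no sensitivity analysis will be carried out for the transcriptomics endpoints". For other data, the preceding paragraph does require analyses with and without outliers.

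The main SAP settles neither point. Section 6.8 names FDR control for the -omics endpoints without a fold-change cut-off, and sections 1, 6.8 and 10 refer the remaining exploratory analyses to an addendum that is not among the documents available.

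**The concern.** The trigger for changing the definition of a positive result is the result itself. A cut-off lowered because effects look weak, or raised because too many genes pass, gives a list whose length and membership partly reflect that choice. A reader of the CSR could not tell what the 1.5-fold rule would have given, because nothing requires those lists to be reported if the cut-off moves.

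The outlier rule has the same weakness. Documenting an exclusion shows that it happened, not what it did to the list.

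Protocol section 11.1 says the systems biology results should generate hypotheses for later studies to verify. A later study needs to know whether the rule that selected the genes was fixed in advance or fitted to the data. The choice also carries into the clustering of DE genes. The goseq pathway enrichment may be affected too, though section 11.4.4 does not state which gene list is its input.

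**Working it through.** **No figure to reproduce.** Protocol section 11.2 refers only to sections 11.1 and 4, so there is no power or error-rate figure for gene expression.

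**Lists governed by the cut-off.** RNA-Seq is done on Days 2, 3, 4, 6, 8, 9 and 15 (Protocol 3.2.3), and arms are pooled before the second dose (11.4.4).
- Versus baseline: 5 pooled days (2, 3, 4, 6, 8) + 2 days (9, 15) × 3 arms = 11.
- Between arms: 3 pairs × 2 days = 6.
- Total: 17.

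**Chance that one gene passes both conditions.** Assumptions, none from the documents: estimated log2 fold change normal around its true value with standard error SE; FDR condition approximated by |z| ≥ 3. That is two-sided p = 0.0027, which Benjamini-Hochberg at 0.05 reaches when about 0.0027/0.05 = 5.4% of genes are rejected.

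A gene must exceed the larger of log2(cut-off) and 3·SE, so

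P(pass) = P(Z > [max(log2 c, 3·SE) − log2(true fold change)] / SE).

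For a true fold change of 1.3: log2 1.3 = 0.3785, log2 1.5 = 0.5850, log2 1.25 = 0.3219.

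| SE | 3·SE | Cut-off 1.5 | Cut-off 1.25 |
|---|---|---|---|
| 0.2 | 0.600 | (0.600 − 0.3785)/0.2 = 1.107 → 13% | same bound, 0.600 → 13% |
| 0.134 | 0.402 | (0.5850 − 0.3785)/0.134 = 1.541 → 6% | (0.402 − 0.3785)/0.134 = 0.175 → 43% |
| 0.1 | 0.300 | (0.5850 − 0.3785)/0.1 = 2.065 → 2% | (0.3219 − 0.3785)/0.1 = −0.566 → 71% |

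SE 0.134 corresponds to 20 subjects with a paired log2 SD of 0.6 (0.6/√20). At SE 0.2 the FDR condition alone already requires an observed fold change of 2^0.6 = 1.52, so lowering the cut-off changes nothing. At smaller SEs the cut-off is the binding condition.

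**List length, by simulation.** Assumptions: 15,000 genes; true log2 fold changes of DE genes drawn from N(0, 0.6); paired t-test with Benjamini-Hochberg at 0.05 in place of edgeR; 20 replicates. Mean number of genes listed:

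| Scenario | 1.3-fold | 1.5-fold | 2.0-fold |
|---|---|---|---|
| n = 20, SD 0.6, 5% DE | 314 | 248 | 80 |
| n = 20, SD 1.0, 5% DE | 116 | 115 | 78 |
| n = 20, SD 0.3–1.5, 10% DE | 454 | 373 | 164 |
| n = 60, SD 0.6, 5% DE | 404 | 256 | 76 |

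Across all scenarios and cut-offs from 1.0 to 2.0, the mean false-discovery proportion was at most 0.054.

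**Sample exclusion, same simulation.** Dropping the 2 most extreme of 20 samples left a Jaccard overlap of 0.69 to 0.91 between the 1.5-fold lists before and after. Dropping 2 of 60 left 0.95 to 0.97. These samples were extreme by chance, so the figures show how sensitive the list is to losing two samples. They do not show the effect of removing a faulty one.

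**The case against.** The strongest reply is that error control is untouched. Only the fold-change filter is open to revision, no sentence makes the 0.05 FDR level revisable, and the simulation shows no rise in the false-discovery proportion. That stands: a reader might infer that FDR control is lost, and neither the documents nor the calculation supports it. What remains is result-driven definition and reporting.

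Second, the effect can be nil. Looking at the fold-change filter alone at SE 0.2, a reader might compute that a true 1.3-fold gene passes 15% of the time at 1.5 and 61% at 1.25. That is not the plan's rule. At that SE an observed 1.25 has z = 0.3219/0.2 = 1.61 and p = 0.107, which cannot meet FDR < 0.05. The objection holds at SE 0.2 but not at 0.134 or 0.1.

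Third, a reader might infer that counts of DE genes will be compared between boosts, or that the cut-off could differ by arm. Section 11.4.4 describes neither. It tests between-group expression directly and speaks of a single cut-off. Nor does it say that the canonical correlation and penalised regression models are limited to DE genes.

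Fourth, exclusions are not unguarded: the meta-data check and CSR documentation are real safeguards. They do not show what an exclusion changed. The stated reason for having no re-analysis is complexity, which has some force for the whole pipeline (clustering, enrichment, cross-validated models) but much less for the DE step alone.

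Finally, the work is exploratory, and the addendum may fix both points.

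**Conclusion.** The point holds as a minor one for the protocol and main SAP. The cut-off may be revised on sight of the effects it filters, with no rule, range or deadline, and outlier exclusions in transcriptomics get no with/without comparison although other endpoints do. Up to 17 exploratory gene lists, and the clustering built on DE genes, can therefore be shaped by their own results.

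The size is conditional. For a true 1.3-fold gene, moving the cut-off from 1.5 to 1.25 has no effect at log2 SE 0.2 and a large one at 0.134 or 0.1. This rests on assumed SEs, a normal approximation, and |z| of about 3 standing in for the FDR condition. If fewer genes are rejected, the implied |z| is higher and the cut-off binds less often.

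It would go too far to conclude that the reported lists will in fact be data-dependent: the revision is permitted, not certain, and the addendum has not been seen. The primary safety and secondary ELISA results are unaffected.

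**What to change.** First check the SAP addendum. If it already fixes the cut-off and the exclusion rule, point to it from the protocol and stop there. Otherwise:

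1. Replace the revision sentence in Protocol section 11.4.4 with: *The 1.5-fold cut-off is fixed and its results will always be reported; results at any other cut-off will be shown beside them and labelled post hoc.*
2. In section 11.4.5, state that sample exclusions are decided blind to arm, and say what happens to an outlier with no experimental explanation.
3. Where any sample is excluded, repeat the main edgeR DE lists with all samples. Clustering, enrichment and the cross-validated models need not be repeated, which meets the complexity argument.

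The cost is wording plus one extra run of the DE step. No visits, samples or subjects change. The team gives up the freedom to replace the 1.5-fold lists, which may be longer or shorter than it would like.

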11.4.5. Missing Values and Outliers

All attempts will be made to collect all data per protocol.

As missing data are expected to be minimal, no imputation will be performed for missing values. Any data point that appears to be erroneous or inexplicable based on clinical judgment will be investigated as a possible outlier. If data points are identified as outliers, sensitivity analyses will be performed to examine the impact of including or excluding the outliers. Any substantive differences in these analyses will be reported.

For the transcriptomics endpoint, extreme data points will be identified by inspecting global patterns in the data. Experimental meta-data will be examined to see whether the outlying pattern can be attributed to experimental error such as sample mislabeling. Excluded outliers will be documented in the CSR. Due to the complexity, no sensitivity analysis will be carried out for the transcriptomics endpoints.

Please see the separate document **“Statistical Analysis Plan”** for additional information.

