7.2. Enrollment/Baseline

Day 1, Visit 1

Sixty subjects who meet all inclusion and no exclusion criteria will be administered study product. The following procedures will occur for all Treatment Arms:

- Subject's willingness to participate will be reconfirmed and documented in the subject's study records prior to performing any further study procedures, including administration of the study vaccine.
- Eligibility criteria, including results of all clinical screening laboratory evaluations, will be reviewed with subjects prior to study vaccination to ensure continued eligibility.
- Complete medical history and any updates obtained by interview of subjects since the screening visit will be reviewed with subjects prior to study vaccination to ensure continued eligibility.
- All concomitant medications will be reviewed with subjects prior to study vaccination for accuracy and completeness. Any new concomitant medications (including non-study vaccines) taken since the screening visit will be reviewed with subjects and assessed for continued eligibility prior to study vaccination. Medications reported in the eCRF are limited to those taken within 30 days prior to study vaccination.
- Vital signs, including oral temperature, pulse, and blood pressure, will be obtained to ensure eligibility. Vital signs assessed on Day 1 prior to the first study vaccination will be considered as baseline. Subjects must not eat or drink anything hot or cold, or smoke within 10 minutes prior to taking oral temperature.
- A targeted physical examination may be performed prior to study vaccination, if indicated based on review of complete medical history and any updates obtained by interview of subjects since the screening visit, by a study clinician licensed to make medical diagnoses and listed on the Form FDA 1572 as the site principal investigator or sub-investigator.

- A urine pregnancy test will be performed within 24 hours prior to study vaccination on all females of childbearing potential. Results must be negative and known prior to randomization and study vaccination.
- Subjects will be enrolled in AdvantageEDCSM and assigned randomly to a treatment arm prior to study vaccination.
- Venous blood will be collected prior to the study vaccination for safety labs (refer to [Section 8.2.1](#)).
- Venous blood will be collected prior to the study vaccination for high resolution HLA typing for Class 1 (A, B, and C locus) testing.

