8.2.2. Special Assays or Procedures

Immunogenicity testing will include the following (post first vaccination):

- Humoral responses by ELISA and ADCC at Day 1, 8, 15, 22, 29 and 36.
- Humoral response by EBOV GP Neut at Day 1, 8 and 15.
- Cell-mediated immunity assays (EBOV GP T cell response) at Day 1, 8, 15, 22, and 36.
- Cell-mediated immunity assays (ChAd3 vector T cell response) at Day 1, 8, 15, 22 and 36.
- Plasmablasts (5), BCR repertoire analysis (11), CD8 tetramer staining and activation marker analysis at Day 1, 8 and 15.
- Cytokine/chemokine measurement at Day 1, 2, 3, 4, 6, 8, 9, and 15.
- Transcriptomics/Gene expression PBMCs at Day 1, 2, 3, 4, 6, 8, 9 and 15.

- Characterization of antigen-specific BCR as measured by yeast display on day 36.

Venous blood samples will also be collected for future use. 8 mL will be collected on Day 1, 8, 15, 22 and 36 post first vaccination. 42 ml will be collected on Day 182 post first vaccination. Collection of future use samples is a condition of participation in this study.

The volume (ml) of venous blood to be collected for immunogenicity assays and future research is presented in [Table 2](#).

Table 2: Blood Volumes (ml)

Study Visit (V)	0	1	2	3	4	5	6	7	8	9	10	11	12	13	14	US	ED
Study Day (from Vaccine 1)	<-29	1	2	3	4	6	8	9	15	22	29	36	76	106	182		
Screening Lab	14.2																
Clinical Safety Evaluations		6.5					6.5		6.5		6.5	6.5				6.5^	6.5^
High Resolution HLA typing for Class 1 (A, B, C locus)		6.0															
Humoral response – ELISA (Op 2)																	
Humoral response – ADCC (Op 7)		10.0						10.0		10.0	10.0						10.0^
Humoral Response, EBOV GP Neut Antibody (Op7a)																	
EBOV GP T cell responses (Op 3)		24.0						24.0		24.0	24.0		24.0				
ChAd3 vector T cell responses (Op 4)																	
Plasmablasts (Op 5, 11)		32.0					32.0		32.0								
Cd8 Tetramer Staining (Op 9)			8.0														8.0*
Activation Marker Analysis (Op 10)								8.0		8.0							
Exploratory cytokine/chemokine (Op 6)		5.0	5.0	5.0	5.0	5.0	5.0	5.0	5.0								
Transcriptomics PMBCs (Op 8)		16.0	16.0	16.0	16.0	16.0	16.0	16.0	16.0								
Yeast Display													16.0				
Future Use		8.0					8.0		8.0	8.0		8.0		42.0			
Total per visit	14.2	115.5	21.0	21.0	21.0	21.0	109.5	21.0	109.5	42.0	16.5	64.5	0.0	0.0	42.0	6.5	14.5-24.5
Running Total	14.2	129.7	150.7	171.7	192.7	213.7	323.2	344.2	453.7	495.7	512.2	576.7	576.7	576.7	618.7	N/A	N/A

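### RNA-Seq mislabelling is looked for only among libraries that appear as global outliers, a rule not designed to catch libraries exchanged between subjects

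*Protocol*

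**What the plan says.** Protocol 11.4.5 sets the rule for the transcriptomics endpoint. First, "extreme data points will be identified by inspecting global patterns in the data". Then: "Experimental meta-data will be examined to see whether the outlying pattern can be attributed to experimental error such as sample mislabeling". Excluded outliers are to be documented in the CSR, but "no sensitivity analysis will be carried out for the transcriptomics endpoints".

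Protocol 11.4.4 names the tools. Principal component analysis, non-metric multidimensional scaling and hierarchical clustering "will be used to identify potential global outliers and systematic batch effect". Sample identity is not among the stated purposes. The negative binomial models then look for genes "for each study group and post-vaccination day that were differentially expressed (DE) compared to pre-vaccination", and for genes that differ between study groups. No pairing or subject term is stated.

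The sampling plan is in Protocol 8.2.2 ("Transcriptomics/Gene expression PBMCs at Day 1, 2, 3, 4, 6, 8, 9 and 15") and 7.2 ("Sixty subjects who meet all inclusion and no exclusion criteria will be administered study product"). Section 7.2 also provides an independent identity reference: "Venous blood will be collected prior to the study vaccination for high resolution HLA typing for Class 1 (A, B, and C locus) testing". SAP 9.1 shows that sex is recorded.

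SAP section 1 places the systems biology analyses in an addendum, which was not among the documents available for this review.

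**The concern.** The Protocol names mislabelling as an error it wants to find, but the search begins only once a library looks outlying. A correct library under the wrong subject's name is an ordinary library, and it looks most ordinary when the two exchanged samples come from the same study day.

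The analyses that most need correct subject labels are those in Protocol 3.2.3 that relate expression changes to each subject's own peak ELISA titer, T-cell response, neutralizing titer or ADCC response. A wrong label there separates predictor from outcome. A wrong Day 1 library is worse, because it enters all seven of that subject's changes from baseline. Protocol 5.4.2 masks the laboratory staff to subject and visit, so they are poorly placed to notice an exchange, and with no sensitivity analysis there is no later point at which it would show.

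**Working it through.** The plan gives no swap rate, power or error figure on this point, so there is nothing of its own to reproduce.

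**Inputs.** From the documents: 60 subjects, 20 per arm (Protocol section 4, Table 1); 8 RNA-Seq days (8.2.2), so 60 × 8 = 480 libraries; arms pooled up to and including Day 8 (Protocol 11.4.4, SAP 6.1), so n = 60 on those days and 20 per arm on Days 9 and 15. Assumed: a random-intercept model on the log scale with within-subject correlation ρ, and the mislabelling rates in step 6.

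**1. What the outlier rule can see.** An exchange permutes two labels and leaves the set of expression profiles as it was. All PCA, scaling and clustering coordinates are therefore identical with and without it. It can show only if the plots are read against labels. A same-day exchange does not show even when they are read by day; they must be read by subject.

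A small idealised simulation agrees (2,000 independent genes, ρ from 0.05 to 0.7, 25 replicates per setting). A global outlier rule flagged 0 to 2% of swapped libraries, against 0.7 to 1.0% of correct ones. Matching each library to its own subject's other libraries, by expression correlation as a stand-in for variant concordance, found 100%.

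**2. Types of exchange**, if any two libraries were exchanged at random, out of 480 × 479 / 2 = 114,960 pairs:
- same day, different subject: 8 × (60 × 59 / 2) = 14,160, or 12.3%
- same subject, different day: 60 × (8 × 7 / 2) = 1,680, or 1.5%
- both different: the remaining 86.2%

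Between-subject exchanges are therefore 98.5% in total.

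**3. Association with the subject's own response.** One same-day exchange within the analysed group makes two of n changes wrong. The covariance is multiplied by 1 − 2/n and the variance of the change by 1 + (2/n) × ρ/(1 − ρ). The correlation is therefore multiplied by (1 − 2/n) / √[1 + (2/n) × ρ/(1 − ρ)].

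| ρ (assumed) | n = 20 | n = 60 |
|---|---|---|
| 0.3 | 0.88 | 0.96 |
| 0.5 | 0.86 | 0.95 |
| 0.7 | 0.81 | 0.93 |
| 0.9 | 0.65 | 0.85 |

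**4. Baseline contrasts, if paired.** A mismatched pair has 1/(1 − ρ) times the variance of a correct one. With k wrong pairs the average variance is multiplied by [n − k + k/(1 − ρ)]/n.

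| ρ (assumed) | n = 20, k = 1 | n = 60, k = 1 | n = 20, k = 2 | n = 60, k = 2 |
|---|---|---|---|---|
| 0.6 | 1.075 | 1.025 | 1.15 | 1.05 |
| 0.8 | 1.20 | 1.067 | 1.40 | 1.133 |
| 0.9 | 1.45 | 1.15 | 1.90 | 1.30 |

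The k = 1 columns are for one wrong library. An exchange within one analysed group gives k = 2. In that case the two errors cancel in the mean log fold change, and only the spread of the changes rises. If the model has no subject term, a same-day exchange within one group leaves the contrast unchanged, because each group-by-day cell holds the same libraries.

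**5. Arm differences.** One same-day exchange between two arms of 20 turns the arm means into (19A + B)/20 and (19B + A)/20. Their difference is (18/20)(A − B), a 10% dilution. For a post-vaccination library this can occur only on Days 9 and 15, since all arms receive the same product until Day 8. Such cases are (2/8) × (40/59) = 17% of same-day exchanges if these fall evenly over days.

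**6. Frequency.** If 0.1%, 0.5% or 1% of libraries were mislabelled, 0.48, 2.4 or 4.8 libraries would be affected, that is 0.24, 1.2 or 2.4 exchanges. On a Poisson count, the chance of at least one exchange is 1 − exp(−0.24) = 21%, 1 − exp(−1.2) = 70% or 1 − exp(−2.4) = 91%. For same-day exchanges alone, at 12.3% of these, it is about 3%, 14% or 26%.

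**The case against.** The strongest objection is the missing document. RNA-Seq quality control would naturally sit in the SAP addendum, and specimen handling in the MOP. Either may already contain an identity check, so the gap is shown only for the Protocol and main SAP. This stands, and the request is conditional on it.

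Three stronger readings are tempting and should be resisted:
- A reader might infer that same-day exchanges are the main type of error. The documents do not say how samples are batched, and under random exchange that type is 12.3%. The remedy does not depend on this, since it addresses all between-subject exchanges.
- A reader might infer that the planned methods cannot find an exchange. Hierarchical clustering with eight libraries per subject could show a misplaced one if read by subject. The fair statement is that the plan does not say it will be.
- A reader might infer that the differential-expression contrasts are paired. The outcome measures speak of change from Day 1, but 11.4.4 states no pairing, so the variance figures are conditional. The figures for an arm of 20 also do not apply to the pooled days.

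It is also fair that the study tests no formal hypothesis (Protocol 11.1) and that general quality control exists (section 13). That quality control is not a test of sample identity.

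**Conclusion.** The point holds in a limited form. Followed as written, the rule examines mislabelling only after an outlying pattern appears, and a between-subject exchange produces none. It would remain unless someone reads the clustering by subject.

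The most direct harm is to the subject-level association analyses. Arm contrasts on Days 9 and 15 can be diluted by about 10% per cross-arm exchange, and baseline contrasts gain variance if they are paired. A reader might infer that mean fold changes within a group are distorted; an exchange within one analysed group leaves them unchanged.

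The sizes rest on assumed within-subject correlations and one exchange, and the frequency of exchanges is unknown. Only exploratory endpoints are concerned; the primary safety and secondary ELISA results are unaffected. This is a cheap improvement rather than a serious defect.

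**What to change.** Confirm whether the SAP addendum has an identity check. If not, add one to Protocol 11.4.4/11.4.5 or the addendum, to be done before modelling and blind to arm:

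1. Variant concordance among each subject's eight libraries, as the main check.
2. Sex-specific gene expression against recorded sex. This is support only: it could reveal at most 30 × 30 / 1,770 = 51% of same-day exchanges with a 50/50 sex split, or 42 × 18 / 1,770 = 43% with 70/30 (assumed splits).
3. HLA alleles called from the reads against the Day 1 Class I typing, which ties the libraries to the named subject.

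Relabel a library only when its true source is proven; otherwise exclude it. Report the numbers relabelled and excluded.

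The cost is computation on existing reads and data plus one paragraph of text, with no new samples or visits. A few libraries may be lost. Exchanges of days within one subject are not covered and stay with the existing pattern inspection.
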